### 3.4.3 Quantitative Assessment of Organizational Factors

During the main phase of the project, OAT site staff and administrators (average N=3 per site) will complete a survey at baseline and the end of follow-up phase. Provider-level Factors will include provider characteristics (e.g., socio-demographics, education and work experience) and their attitudes toward SHIM (or a theoretical integrated HCV care model at the SOC sites) and their

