In the second part of the analysis, we will examine the role of barriers and facilitators measured using the multi-level framework that includes client-, provider-, organizational-, community-level variables. First, using principal component analysis (PCA), we will identify various dimensions of clinician and organizational behavior that might influence HCV care integration into OAT settings through adoption and implementation of SHIM +/- ECHO at each site, which would summarize the variability in the data. PCA, a transformation used for data reduction, will be applied to multi-level organizational variables. Each principal component represents a different weighted average of the various organizational and client level variables, and each explains a different aspect of the variation observed in patterns of the organization and staff member. Principal components are important ways to group variables that are independent of each other by design, which addresses the issue of multicollinearity [33, 34], which can undermine various modeling strategies. To test the extent to which the barriers and facilitators are associated with higher or even increasing HCV diagnosis, treatment initiation and SVR achievement, we would estimate, using a generalized linear mixed model in which the outcome would be measured at the patient level (level 1), as a dichotomous variable of having been diagnosed/treated/cured or not. Among the covariates in the model, we would include an additional parameter that would incorporate the random effects associated with each provider (level 2), and a random effect associated with each site (level 3), which would be modeled as a function of estimated barrier and facilitator principle components.

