### 3.5.1 Design overview

Individual randomization of subjects within each site would likely lead to a high degree of cross-contamination between the study groups because the selected interventions are designed to sustainably change the provider knowledge and practice. Therefore, we have chosen a cluster-randomized trial design, where participating sites will be randomly assigned to one of the three implementation arms. Based on our preliminary studies suggesting region-specific differences in HCV level among OAT patients, we will stratify 12 OAT sites by 4 defined geographic regions (Center, East, South, West) at a 1:1:1:1 ratio. To achieve the desired sample size (see Sample Size section) and retain equal size in each group, we will select and match 3 clinics across the 4 regions. One clinic per triplet will be randomized to one of the three arms: Standard of Care, SHIM and SHIM+ECHO (see Study Conditions), resulting in total 4 clinics per arm. Each clinic will aim to recruit 40 patients. In case of clinic's capacity the availability of DAA medication in region, the clinic's capacity to include in treatment and monitor the course of treatment of a larger number of patients) the number of participants can be increased up to 60). All sites will follow the same patient recruitment and data collection procedures.

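### The Aim 2 components combine organizational and client variables and then model the site effect, so patient-level and clinic-level associations are not separated and the site-level part rests on 12 clinics

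*Combined protocol and SAP*

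**What the plan says.** Section 3.4.4 describes the second part of the Aim 2 analysis in three steps.

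- Data reduction: "PCA, a transformation used for data reduction, will be applied to multi-level organizational variables". The next sentence widens the input: "Each principal component represents a different weighted average of the various organizational and client level variables".
- Outcome model: "using a generalized linear mixed model in which the outcome would be measured at the patient level (level 1"), with a provider random effect at level 2.
- Use of the components: "a random effect associated with each site (level 3), which would be modeled as a function of estimated barrier and facilitator principle components".

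The numbers of units come from other sections. Section 3.5.1 gives the clinics, "we will stratify 12 OAT sites by 4 defined geographic regions (Center, East, South, West) at a 1:1:1:1 ratio", and the patients, "Each clinic will aim to recruit 40 patients", with an allowance of up to 60. Section 3.4.3 gives the staff data: "OAT site staff and administrators (average N=3 per site) will complete a survey at baseline and the end of follow-up phase". It adds that several short scales are repeated twice a year.

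Section 3.4.4 does not state whether a PCA row is a clinic, a staff member or a patient. It also does not say whether client variables are averaged or centred within clinic, how many components are kept, or how their stability is checked.

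**The concern.** A site effect has one value per clinic. A component that loads on client variables has, on the literal reading, one value per patient. Using the second to model the first leaves open which association is being estimated: that patients with a given profile do worse, or that clinics with many such patients do worse. These are different findings with different remedies.

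The second difficulty is the number of clinics. Clinic characteristics such as budget or staffing supply 12 values, whatever the number of patients. A PCA on so few units can produce a dominant component from unrelated variables.

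What is at stake is the interpretation of Aim 2. Section 3.4.1 says the merged data will inform scale-up. A patient characteristic, or an accident of these 12 clinics, could be reported as an organizational barrier.

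**Working it through.** **1. The plan's own figure.** Section 3.4.5 supports the Aim 2 analysis with 900 patients. The design gives 12 × 40 = 480, or 12 × 60 = 720 at most, so 900 is not reproduced. More to the point, it counts patients. The site-level part has 12 clinics and about 12 × 3 = 36 staff respondents.

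**2. Level of a component score.** For patient *i* in clinic *j*, score = a × (organizational values of clinic *j*) + b × (client values of patient *ij*). If b is not zero and client values are not averaged, the score varies within clinic *j*, whereas the site effect does not.

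**3. Size of the blending.** Let λ be the share of a covariate's variance that lies between clinics. A single pooled slope is then about λ × (between-clinic slope) + (1 − λ) × (within-clinic slope). Take a between-clinic slope of 1 and a within-clinic slope of 0. Simulation with 12 clinics gives:

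| Assumed ICC of covariate | Pooled slope |
|---|---|
| 0.05 | 0.04 |
| 0.2 | 0.18 |
| 0.5 | 0.47 |

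The pooled slope equals neither true slope. If client variables are first averaged to clinics, the fit is between-clinic only and this problem does not arise.

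**4. Patient-row PCA on pure noise.** The numbers of variables and the ICCs are assumptions; the documents give none.

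- With 10 clinic variables copied to every patient, 10 client variables, 12 × 40 patients and client ICC 0.05, the first component explains 14.6% of variance, against 6.9% with 480 independent rows. Clinic variables supply 95% of its squared loadings. Components 4 to 8 have on average 30% to 84% of their variance within clinics.
- With 8 clinic and 5 client variables and ICC from 0 to 0.2, the first component takes 90–99% of its squared loadings from clinic variables, and 97–99% of its score variance lies between clinics. For the fourth component, 36–68% lies between clinics.

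**5. PCA on 12 clinic rows, pure noise.** The true share is 1 divided by the number of variables.

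| Variables | First component, share of variance | True share |
|---|---|---|
| 6 | 35% | 17% |
| 10 | 28% | 10% |
| 15 | 24% | 7% |
| 20 | 22% | 5% |

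The mean absolute correlation between two unrelated variables is 0.25 with 12 rows and 0.04 with 480.

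**6. Does real structure survive?** The check is the median agreement (absolute cosine) of first components from two independent sets of 12 clinics, with 10 to 15 variables. It is 0.18–0.22 with no structure, 0.39 with loadings of 0.5 on half the variables, and 0.72 with loadings of 0.7.

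**7. Information left at site level.**

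- If region and arm are also in the site-level model, 12 − 1 − 3 − 2 = 6 degrees of freedom remain, and 3 after three components.
- Without those terms, the chance R² across 12 sites averages k/11 for k components: 1/11 = 9% for one and 3/11 = 27% for three.
- A simple site-level correlation needs |r| ≥ 0.58 for p < 0.05. Power at r = 0.5 is Φ(3 × atanh 0.5 − 1.96) = Φ(−0.31), about 38%.

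**The case against.** The strongest reply is that the plan does not describe a PCA on 480 patient rows. Most of the wording in section 3.4.4 concerns clinician and organizational dimensions, and client variables appear in one clause. If they are averaged to clinics, the blending disappears. This stands as far as it goes: the patient-row layout is the literal reading, not stated text. The 12-unit limit remains on the other reading.

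A reader might infer four stronger things that the documents do not support.

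- *That all organizational inputs have only 12 distinct values.* Attitude and readiness scales come from about 36 staff, some repeatedly. Only items such as budget or staffing have one value per clinic.
- *That a patient-varying component cannot explain a site effect.* It can, through case mix, if its mean differs between clinics. The difficulty is narrower: unequal within- and between-clinic slopes. No calculation here shows opposite signs.
- *That the components will be chance patterns.* This is a risk, not a certainty. Section 3.4.4 expects some scales to be collinear, and strong structure is partly recovered from 12 clinics.
- *That the Aim 3 result is compromised.* The primary comparison does not use these components. Section 3.5.8 lists Aim 2 measures as covariates, not PCA scores.

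It is also fair that the two problems fall mostly on different components: in the simulations the first is almost wholly between clinics, and the mixing affects later ones, which may not be retained. Section 3.4.4 already describes the analyses as exploring, although it also speaks of testing associations. The random effects in the model address correlation of outcomes; they neither stabilise loadings nor separate the two slopes.

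**Conclusion.** The point holds in limited form. Section 3.4.4 states a method that combines levels and applies the result to the site effect, so this is more than missing detail. Followed literally, it leaves patient-level and clinic-level associations in one coefficient. On either reading, site-level components come from 12 clinics and about 36 staff, and their loadings can largely reflect chance unless the true structure is strong.

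The counts of 12 clinics and about three staff per clinic come from the protocol. The simulated sizes rest on assumed numbers of variables, ICCs and loadings, and mostly on pure noise, so they show what can happen, not what will. The effect is confined to the largely exploratory Aim 2 analysis. The plan should be changed, but the trial's main comparison is not at risk from this step.

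**What to change.** Revise section 3.4.4 as follows.

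- State the row unit of each PCA.
- Reduce clinic and staff scales separately from client variables, or replace the components with pre-specified scale scores.
- Enter client variables or components at level 1 as within-clinic deviations, with their clinic means as separate terms.
- Allow only one or two pre-specified clinic-level components or scale scores to predict the site effect.
- State that site-level inference rests on 12 units and is exploratory.

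This separates the levels. It limits, but does not remove, the instability that comes from having 12 clinics: a PCA on 12 clinic means has the same chance correlations as one with clinic values copied to equal numbers of patients.

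The cost is SAP wording, slightly more analysis work, and fewer organizational components to report. No new data are needed.

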#### 3.4.5 Power Analysis

The qualitative sub-study sample during the pilot phase will be limited to one focus group with patients and three in-depth interviews with providers.

In the main phase, we will conduct two focus groups with 6-8 patients, one in-depth interview with participant who have dropped out of treatment, or not completed SVR12 testing, or didn't start treatment, two in-depth interviews with 2-4 providers.

In order to conduct the proposed analysis, a sample size of 900 patients, provides more than sufficient power to conduct the proposed analyses. The use of principal component analysis (PCA), for parsimoniously grouping variables is a reductionist strategy to explain groupings of variables with multiple collinearity. The time-dependent analysis allows for detection of even small changes in the primary and secondary outcome, even if the primary (or secondary) outcome increases any of the study groups. Thus, as few as 200-300 participants in each group is more than sufficient to achieve sufficient power (>0.95) to detect an intervention effect, including a synergistic effect of intervention^[No ECHO] x intervention^[ECHO] and even by site type (by varying degrees of integration), over time.

### 3.5 Research methods for Aim 3

Aim 3: To evaluate the effectiveness of SHIM in improving the HCV treatment cascade outcomes using a cluster-randomized three-arm trial design in 480 HCV-infected patients at 12 OAT clinics

randomized to standard of care (N=160) versus SHIM with (N=160) or without (N=160) ECHO facilitation.

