### 3.5.2 Site eligibility and selection

To participate in the study, each OAT site will need to meet the following criteria: (a) at least 100 patients receiving OAT; and (b) regional administrator approval for the site to receive the DAA medications and its clinicians to participate. Before the start of the first year of the main phase of the project there were 202 OAT sites in Ukraine, with 34 having over 100 patients (12, 10, 7, 5 sites in Center, East, South, West, respectively) and 21 have over 150 patients. OAT sites are minimally staffed with 1 narcologist and two nurses; the number of counselors and case managers may vary. After we define the three sites from each region, we will randomize them into one of the three study arms.

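### Aim 2 power is argued from 900 patients the trial cannot enrol, while barrier and facilitator components placed on the site effect have only 12 clinics behind them

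*Combined protocol and SAP*

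**What the plan says.** **Model (3.4.4).** Each cascade outcome is binary at patient level. The model adds "the random effects associated with each provider (level 2), and a random effect associated with each site (level 3"), and the site effect is regressed on principal components summarising barriers and facilitators. The components may mix organisational and client-level variables. The section describes the work as exploratory in its opening, but later speaks of testing the associations.

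**Power (3.4.5).** The plan states that "a sample size of 900 patients, provides more than sufficient power to conduct the proposed analyses" and that "as few as 200-300 participants in each group is more than sufficient to achieve sufficient power (>0.95) to detect an intervention effect". It gives no effect size, significance level, intracluster correlation (ICC), or number of clinics or providers.

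**Design.** The Aim 3 statement opening section 3.5 describes a "cluster-randomized three-arm trial design in 480 HCV-infected patients at 12 OAT clinics", and section 3.5.1 has one clinic per regional triplet going to each arm, "resulting in total 4 clinics per arm". The target is 40 patients per clinic, with up to 60 where drug supply and capacity allow.

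**Staff.** Section 3.5.2 notes that "OAT sites are minimally staffed with 1 narcologist and two nurses". Section 3.4.3 says that "OAT site staff and administrators (average N=3 per site) will complete a survey", which is about 36 respondents. Neither section says how many treating providers the 12 sites have, or whether nurses count as providers.

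**The concern.** Two things do not fit. First, the 900 patients do not correspond to any enrolment that section 3.5.1 permits. Second, a patient count is the wrong basis for a predictor that takes one value per clinic. More patients per clinic sharpen each clinic's own rate, but they add no clinics over which the predictor can vary.

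A reader who takes "provides more than sufficient power to conduct the proposed analyses" at face value would read a null result for, say, organisational readiness as evidence that readiness does not matter. With 12 clinics such a null would be the likely result even for a substantial association.

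The provider level raises a separate, smaller problem. Where one provider treats everyone at a site, provider and site are the same grouping, so the plan asks for a variance split that those sites cannot inform. The plan has no rule for this case.

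**Working it through.** **Inputs from the documents.** 900 patients, 200-300 per group and power above 0.95 (3.4.5); 12 clinics, 4 per arm, 40 to 60 patients each, 4 regions (3.5.1); two-sided 5% (3.5.8, stated for Aim 3; Aim 2 states none); standardized effect size 0.20 (3.5.9, Aim 3). **Assumed, because the documents give none:** site-level correlation r of 0.5 or 0.7, and ICC of 0.05 to 0.20.

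**1. The plan's own figure.** It cannot be reproduced, since Aim 2 states no effect size. Borrowing 0.20 from Aim 3, a three-group chi-square test (2 df) with noncentrality N × 0.20² gives:
- N = 600: noncentrality 24, power 0.995
- N = 900: noncentrality 36, power above 0.999
- N = 480: noncentrality 19.2, power 0.98

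So a figure above 0.95 is attainable if patients are treated as independent. With 40 per clinic the design effect is 1 + 39 × ICC. At ICC 0.05, 0.10 and 0.20 it is 2.95, 4.9 and 8.8. The effective size of 480 becomes 163, 98 and 55, and power 0.62, 0.41 and 0.24, before any small-cluster correction. This check concerns an intervention effect, which is what the >0.95 sentence names. It does not address barrier and facilitator associations.

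**2. Attainable enrolment.** Planned: 12 × 40 = 480, or 160 per arm. Ceiling: 12 × 60 = 720, or 240 per arm. Reaching 200 per arm needs an average of 50 per clinic; 300 per arm and 900 in total are out of reach.

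**3. Power for one site-level component.** With n = 12 clinics and k adjustment degrees of freedom (arm 2, region 3), Fisher's z gives δ = arctanh(r) × √(n − 3 − k) and power ≈ Φ(δ − 1.96) + Φ(−δ − 1.96). A simulated t-test on n − 2 − k df is shown alongside.

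| Adjustment | k | δ at r = 0.5 | Power at r = 0.5 (z / t) | Power at r = 0.7 (z / t) |
|---|---|---|---|---|
| None | 0 | 0.549 × 3 = 1.65 | 38% / 40% | 74% / 78% |
| Arm | 2 | 0.549 × √7 = 1.45 | 31% / 33% | 63% / 68% |
| Arm and region | 5 | 0.549 × 2 = 1.10 | 20% / 21% | 41% / 46% |

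Noncentral-t versions at r = 0.5, with the usual choices of noncentrality, run from about 18% (5 df) to about 44% (10 df), so the method matters little.

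The correlation needed for 80% power is r = tanh(2.80 / √(n − 3 − k)): tanh(2.80 / 3) ≈ 0.73 unadjusted and tanh(2.80 / 2) ≈ 0.89 with arm and region.

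**4. Adding patient-level noise.** Step 3 treats each clinic's underlying rate as known. A simulation of 12 clinics with binomial outcomes, analysed as clinic log-odds on clinic degrees of freedom, gives at r = 0.5 over ICC 0.05 to 0.20:

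| Patients per clinic (total) | Unadjusted | Arm and region |
|---|---|---|
| 40 (480) | 25-34% | 13-18% |
| 60 (720) | 28-36% | 15-19% |
| 75 (900) | 31-37% | 15-19% |

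The last row is the decisive one: even if 900 patients could be enrolled at these 12 clinics, power would barely move.

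**5. Provider versus site.** Let the provider and site variances be σ²p and σ²s. With one provider at a site, every pair of patients there has covariance σ²p + σ²s. Setting (σ²p, σ²s) to (0.3, 0.1) or (0.1, 0.3) gives the same covariance matrix, so only the sum is identified. With two providers, pairs sharing a provider have σ²p + σ²s and other pairs have σ²s; the two settings then differ, and the split is identified in principle.

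**6. Reference distribution.** The plan states no denominator degrees of freedom. If a site-level coefficient were referred to the normal distribution, the chance of |t| > 1.96 under the null would be about 11% on 5 df and about 8% on 10 df, against a nominal 5%.

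**The case against.** Several points on the other side stand.

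- **The power figure is conditional.** The model in 3.4.4 lists neither arm nor region. Section 3.4.1 supports regional control of community factors, but arm adjustment is an assumption, and so is r = 0.5. A reader might infer that power simply is 20-25%; the documents fix no single value. At r = 0.7 without adjustment it is 74-78% before patient-level noise.
- **Not every barrier is a clinic-level variable.** Trust in physician, stigma and social support are collected from each patient (3.5.6), and staff scales come from about 36 respondents, some of them repeatedly. It would be wrong to say that all barriers and facilitators vary over only 12 clinics. The limit applies to components entered on the site effect.
- **Single-physician sites are not documented.** Section 3.5.2 gives a staffing minimum, and trial sites need at least 100 OAT patients. One may not conclude that many of the 12 have only one physician.
- **Non-convergence is not shown.** Where provider and site coincide, the total variance is still identified, and an arbitrary split need not distort the component coefficients. The damage is mainly to the variance partition.
- **Patients are not treated as independent in the model.** The site random effect already guards against that. What remains is the unstated small-cluster reference distribution.
- **More scales than clinics in the PCA** is also not established: 3.4.3 gives no count of variables, and 3.4.4 does not fix the unit of the PCA.

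The exploratory label in 3.4.4 lowers the stakes. It does not rescue the power claim in 3.4.5, whose first sentence covers all the proposed analyses.

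**Conclusion.** The point holds in bounded form. Section 3.4.5 rests Aim 2 power on a sample 180 above the trial's ceiling (900 − 720) and 420 above its target (900 − 480), and on the wrong unit for site-level components. For such a component, with r = 0.5 assumed and two-sided 5%, power is about 40% unadjusted, about 20% adjusted for arm and region, and 13-18% adjusted with 40 patients per clinic and an assumed ICC of 0.05 to 0.20. None of the r = 0.5 scenarios examined comes near the stated 0.95. Only very strong associations, r of about 0.73 to 0.89, would reach 80%, and that is before patient-level noise.

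The provider and site variances are inseparable at any site with one treating provider. How often this arises cannot be told from the documents. Client-level predictors fall outside the 12-clinic limit.

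**What to change.** **In 3.4.5:** replace 900 with the actual sample (480 planned, up to 720). Withdraw the sufficiency and >0.95 statements for site-level organisational factors. State that these analyses rest on 12 clinics, and give the power range above together with the assumed correlation, adjustment and ICC.

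**In 3.4.4:**
- Define provider and report the number of treating providers at each site.
- Merge level 2 into the site effect unless sites have two or more treating providers.
- Test site-level components against clinic-based, small-cluster degrees of freedom.
- Limit the model to one or two components named in advance.
- Report site-level associations as exploratory estimates with intervals.

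The cost is SAP wording and a simpler model, with no new data collection. The downside is that the organisational findings will be reported with less certainty than the plan now promises.
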